### **8.3.2 Durvalumab and Tremelimumab Dose Modification Not Due to Treatment-related Toxicities**

Durvalumab and tremelimumab administration may be modified or discontinued as a result of events other than toxicity, e.g., intercurrent illness or logistical/administrative reasons, whereby the following rules should apply:

CONFIDENTIAL

1. The originally planned visit/treatment schedule should be maintained in general, i.e., dosing interruptions should not reset the original treatment schedule. Exceptions may be made only for individual dosing days, whereby the interval between any two doses shall be no less than 21 days. All resulting protocol deviations should be documented.
2. If the dosing interruption causes 2 consecutive planned doses to be missed, the treatment should be discontinued.
3. If the dosing interruption is  $\leq$  half the planned dosing interval, the originally planned dose should be given and the next dose(s) should be adjusted in accordance with #1, if necessary.
4. If the dosing interruption is greater than half the planned dosing interval, the dose should be skipped and the next dose(s) should be adjusted in accordance with #1, if necessary.

---

CONFIDENTIAL

## 8.4 BI 1361849 Toxicity Management and Dose Modification

If a toxicity occurs that requires toxicity management in accordance with Sections 8.3 or 8.4, and the toxicity causing drug can be clearly identified, then the respective guideline should be followed. If the toxicity causing drug cannot be identified, then the more conservative guideline should be followed.

In case of adverse events considered related to BI 1361849 or to the combination of BI 1361849 with durvalumab or with durvalumab and tremelimumab, treatment with the vaccine (or with the vaccine as well as durvalumab and/or tremelimumab) may have to be withheld. If a subject experiences any  $\geq$  CTCAE Grade 3 treatment-related AE not fulfilling the criteria for permanent discontinuation, study drug treatment may be resumed after the toxicity has returned to baseline or Grade  $\leq$  1 within a time period  $\leq$  4 weeks for vaccination. No dose reduction of the vaccine dose is foreseen.

Administration of BI 1361849 must be withheld in the following cases and may be postponed to later time points within the allowance windows defined in the table below:

- Subject has fever  $\geq$  38.5 °C or other signs of an acute systemic infection on the day of administration.
- Subject has a suspected autoimmune disease - in this case BI 1361849 should be omitted until the diagnosis is confirmed or excluded. In case of a confirmed autoimmune disease the Sponsor should be contacted to decide whether BI 1361849 should be permanently discontinued.
- Subject has ongoing BI 1361849 related systemic toxicity of initially CTCAE grade 3 or higher that has not yet resolved to at least grade 1 or baseline.
- Subject has a suspected pneumonitis or other interstitial lung disease (ILD). In this case BI 1361849 should be omitted until the diagnosis is confirmed or excluded. In case of confirmed pneumonitis or other ILD, BI 1361849 should be discontinued.
- Subject has an important medical event that in the investigators opinion might be worsened by the administration of BI 1361849 (e.g. acute cardiac events that may deteriorate in case of fever induced by BI 1361849).

Vaccinations should always be administered within the planned time windows given in Section 3.2. However, vaccinations may have to be delayed to allow for recovery of AEs prior to continuation of vaccine treatment. For these circumstances, maximal allowance windows have been specified below. After the delayed vaccination all subsequent vaccinations must be continued within the schedule relative to the first vaccination presented in the flow chart. If a vaccination cannot be administered within the maximal allowance windows for an administration time point, the vaccine administration for this time point has to be omitted, and further vaccinations should be given at subsequent planned time points according to the flowchart in Section 3.2.

---

CONFIDENTIAL

Maximal allowance windows due to AEs:		
Vaccination	Scheduled Week (Day 1 of)	Total extended visit window from originally scheduled vaccination (days)
2 nd	2	3
3 rd , 4 th , 5 th , 6 th , 7 th	3, 5, 7, 9, 11	7
8 th , 9 th	13, 17	10
10 th and continuing	21, 27 and every 6 weeks	28

In the event that prior to a planned blood sampling time point for immunomonitoring, the immediately preceding vaccination has to be delayed or omitted, the blood sampling has to be delayed in the same fashion to ensure that the blood sample has been obtained within 7 ± 2 days after the immediately preceding vaccination. In the event that the vaccination had to be omitted, blood sampling should occur after the next subsequent vaccine administration.

The following toxicities prohibit continuation of study treatment:

- Grade ≥ 3 study treatment-related anaphylactic reactions.
- Study treatment related AEs that are potentially life threatening or may result in permanent disability.
- Grade ≥ 3 pneumonitis/inflammatory lung disease, or other ILD
- Grade ≥ 3 study treatment-related AEs not recovering to baseline or grade 1 within 4 weeks in case of vaccination. The Sponsor should be contacted in case it is considered justifiable to continue treatment at a later time point, to approve continuation of treatment of BI 1361849, which in any case must not occur before the AE finally has resolved or recovered to baseline or grade 1.
- Grade ≥ 3 study treatment-related AEs that reoccur after re-exposure to BI 1361849 (with the exception of local reactions at individual injections sites if they are considered tolerable by the investigator and the patient).

Note: After occurrence of related grade 1 or 2 anaphylactic reactions, a re-exposure may be considered, at the investigator's discretion, if anti-allergic premedication will be added (antihistaminergic agents and/or a steroid). A minimal acceptable allergy prophylaxis regimen will be 50 mg oral prednisone, to be taken at 13 hours, 7 hours and 1 hour prior to vaccination (or other equivalent) and/or 50 mg diphenhydramine i.v. 1 hour prior to vaccination (or other equivalent).

CONFIDENTIAL

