### 3.1.9 DLT and MTD/RCD for the Combination Therapy

MTDs will not be determined in this study. Instead, RCDs will be determined in the context of the predefined dose levels used during the dose evaluation phase as per Section 3.1.7.1.

DLTs will be observed over a period of the first 2 cycles of the combination therapy, including the pre-dose assessment for Cycle 3, defined as the **DLT Evaluation Period**. The decisions for dose evaluations, de-escalations and RCD, as described in Section 3.1.7.1 will primarily be based on the number of subjects with DLTs occurring during the DLT Evaluation Period. DLTs occurring outside the DLT Evaluation Period will also be evaluated and may impact such decisions.

DLTs are defined as any adverse events that are possibly, probably, or definitely related to the administration of durvalumab, tremelimumab, or BI 1361849 components, and fulfill any of the following criteria:

1. Any Grade  $\geq 3$  colitis, pneumonitis, neurological event or uveitis.
2. Any Grade 2 pneumonitis, neurological event or uveitis, with the following exception:
  - Grade 2 pneumonitis, neurological event or uveitis that downgrade to Grade  $\leq 1$  within 3 days after onset, whereby maximal supportive care, including systemic corticosteroids, is permitted.
3. Any *other* Grade  $\geq 3$  toxicity, with the following exceptions:
  - Grade 3 irAEs that downgrade to Grade  $\leq 2$  within 3 days, or to Grade  $\leq 1$  or baseline within 14 days after onset, whereby maximal supportive care, including systemic corticosteroids, is permitted.
  - Grade 3 endocrinopathy that becomes asymptomatic when managed with or without systemic corticosteroid therapy and/or hormone replacement therapy.
  - Grade 3 inflammatory reaction attributed to a local antitumor response (e.g., inflammatory reaction at sites of metastatic disease, lymph nodes, etc.).
  - Grade 3 fatigue for  $\leq 7$  days.
  - Grade 3 infusion-related reaction (first occurrence and in the absence of steroid prophylaxis) that resolves within 6 hours with appropriate clinical management.
  - Liver transaminase elevation  $\leq 8$  times ULN that downgrades to Grade  $\leq 2$  ( $\leq 5$  times ULN) within 7 days after onset, whereby maximal supportive care, including systemic corticosteroids, is permitted.

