  - Total bilirubin  $\leq 5$  times ULN that downgrades to Grade  $\leq 2$  ( $\leq 3$  times ULN) within 7 days after onset, whereby maximal supportive care, including systemic corticosteroids, is permitted.
  - Grade  $\geq 3$  neutropenia that (1) is not associated with fever or systemic infection, (2) does not require medical intervention, and (3) improves to Grade 2 within 7 days.
  - Grade 3 and 4 lymphopenia.
  - Grade 3 thrombocytopenia that (1) is not associated with clinically significant bleeding, (2) does not require medical intervention, and (3) improves to Grade 2 within 7 days.
  - Isolated Grade 3 electrolyte abnormalities that are not associated with clinical signs or symptoms and are reversed with appropriate maximal medical intervention within 3 days.
  - Any pre-existing laboratory abnormality that deteriorates to Grade 3/4, but where the increment of deterioration is considered not clinically significant by both investigator and sponsor.
  - Grade 3 or 4 asymptomatic increases in amylase or lipase levels for which appropriate evaluation shows no clinical evidence of pancreatitis.

Immune-related AEs (irAEs) are defined as AEs of immune nature (i.e., inflammatory) in the absence of a clear alternative etiology. In the absence of clinical abnormality, repeat laboratory testing will be conducted to confirm significant laboratory findings prior to designation as a DLT.

While rules for adjudicating DLTs are specified above, an AE that is Grade < 3 or listed as exempt above may also be defined as DLT after consultation with the sponsor and Investigators, based on the emerging safety profiles of durvalumab, tremelimumab, and BI 1361849. Likewise, subjects who become not evaluable for DLT, because they discontinued or interrupted treatment due to toxicities other than DLTs, may be counted as DLT subjects, if the toxicities cannot be managed in accordance with the dosing modifications described in Section 3.1.8.

Subjects who experience a DLT will be discontinued from study treatment and will enter the On Study and Post Study Follow-up (see Section 3.1.16). However, if it is in the best interest of the subject, the Investigator, subject and Sponsor may agree to continue treatment with BI 1361849.

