- In general, hold M and T until resolution to  $\leq$  Grade 1 and after the end of any steroid taper, and discontinue M and T permanently if such resolution does not occur within 60 days (30 days for neurotoxicities). Criteria for temporary hold or permanent discontinuation of M and T may differ by event as detailed below.
- For *myositis/polymyositis*, hold M and T until resolution to  $\leq$  Grade 1; permanently discontinue M and T if it does not resolve to  $\leq$  Grade 1 within 30 days or if there are signs of respiratory insufficiency.
- For *pneumonitis/interstitial lung disease and myocarditis*, the decision to reinitiate M and T upon resolution shall be based upon treating physician's clinical judgment (as long as the event does not meet DLT criteria).
- For *peripheral neuromotor syndromes*, such as *Guillain-Barre* and *Myasthenia Gravis*, follow general instructions above, but always discontinue M and T permanently if there are signs of respiratory insufficiency or autonomic instability.
- For *endocrinopathies, other than isolated hypothyroidism and isolated Type 1 diabetes mellitus*, follow general instructions above, but subjects may be retreated if the endocrinopathy is controlled and the subject is clinically stable while requiring steroid doses of  $\leq$  10 mg/day prednisone equivalent.
- For *isolated hypothyroidism* managed with hormone replacement therapy, *isolated Type 1 diabetes mellitus* treated with appropriate diabetic therapy, and for *sensory neuropathy/neuropathic pain*, holding M and T is at the discretion of the Investigator.
- For *elevated creatinine* or *rash*, M and T should be held until resolution to  $\leq$  Grade 1 or baseline and after completion of steroid taper.
- For *vitiligo*, no dose modification required.

## Grade 3

- In general, hold M and T until resolution to  $\leq$  Grade 1, and after the end of any steroid taper, and discontinue M and T permanently if such resolution does not occur within 60 days (30 days for neurotoxicities and rash). Criteria for permanent discontinuation of M and T may differ by event as detailed below.
- For *myositis/polymyositis*, follow Grade 2 instructions above.
- For *peripheral neuromotor syndromes* (such as *Guillain-Barre* and *Myasthenia Gravis*), apply respective Grade 2 rules.
- For *endocrinopathies*, follow Grade 2 instructions above.
- For *diarrhea/colitis*, permanently discontinue M and T if toxicity does not improve to  $\leq$  Grade 1 within 14 days.

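### After a DLT, Section 3.1.9 lets BI 1361849 continue by agreement, while Section 8.4 ends it for confirmed pneumonitis/ILD and bars treatment at Grade 3 or higher; neither section says which prevails

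*Protocol*

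**What the plan says.** Protocol Section 8.4 contains two lists that bear on the vaccine after lung toxicity.

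- The first opens with "Administration of BI 1361849 must be withheld in the following cases and may be postponed to later time points within the allowance windows". Its pneumonitis item tells sites to omit the vaccine while the diagnosis is open, and then says: "In case of confirmed pneumonitis or other ILD, BI 1361849 should be discontinued". It states no grade and no relatedness condition.
- The second opens with "The following toxicities prohibit continuation of study treatment". It includes Grade 3 or higher treatment-related anaphylactic reactions and "Grade ≥ 3 pneumonitis/inflammatory lung disease, or other ILD".

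Section 3.1.9 defines the DLTs. They must be possibly, probably or definitely related to one of the study drugs. The first criterion is Grade 3 or higher "colitis, pneumonitis, neurological event or uveitis". The second begins "Any Grade 2 pneumonitis, neurological event or uveitis, with the following exception"; the exception covers events that fall to Grade 1 or lower within 3 days. The third takes in other Grade 3 or higher toxicity, with listed exceptions.

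After a DLT, Section 3.1.9 discontinues study treatment. It then adds that, where this is in the subject's best interest, "the Investigator, subject and Sponsor may agree to continue treatment with BI 1361849". Section 3.1.10 lists a DLT among the reasons for withdrawal from treatment and refers to 3.1.9. Its closing line refers to 8.3 and 8.4 for withdrawals that follow from required interruptions or discontinuations.

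**The concern.** The same event can fall under a rule that stops the vaccine and a rule that lets it continue. The sentence in 3.1.9 is open to every type of DLT and does not mention 8.4. The lists in 8.4 do not mention the agreement route in 3.1.9. When a subject has pneumonitis that qualifies as a DLT, those deciding on the next vaccination can cite the protocol for either course.

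This matters for safety. Pneumonitis is named as an adverse event of special interest in Section 7.1.8, and a history of pneumonitis or ILD excludes a subject under Section 5.2. Whether a subject may be re-exposed to one of the study drugs after such an event should not depend on which section is read first. It also leaves no clear standard for judging whether a continued vaccination was a protocol deviation.

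**Working it through.** No arithmetic applies. The check sets the vaccine rules side by side, for confirmed pneumonitis related to study drug and for the anaphylactic reactions.

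| Event | 8.4, first list | 8.4, second list | 3.1.9 | 8.4 against 3.1.9 |
|---|---|---|---|---|
| Pneumonitis, Grade 1 | Discontinue vaccine | Not named | Not a DLT by the listed criteria | No conflict |
| Pneumonitis, Grade 2, to Grade 1 or lower within 3 days | Discontinue vaccine | Not named | Excepted, not a DLT | No conflict |
| Pneumonitis, Grade 2, not down within 3 days | Discontinue vaccine | Not named | DLT; vaccine may continue by agreement | Conflict |
| Pneumonitis, Grade 3 or higher | Discontinue vaccine | Continuation barred | DLT; vaccine may continue by agreement | Conflict |
| Related anaphylactic reaction, Grade 3 or higher | No specific item | Continuation barred | Can be a DLT under the third criterion; vaccine may then continue by agreement | Conflict when it is a DLT |

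The last row says can be because 3.1.9 excepts some Grade 3 reactions, such as a first infusion-related reaction without steroid prophylaxis that resolves within 6 hours.

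Three places might settle the conflict.

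1. **Section 3.1.8, repeated in 8.3 and 8.4.** If the causative drug is known, its guideline applies; if not, the more conservative of the two applies. This chooses between 8.3 and 8.4. It does not rank 8.4 against 3.1.9.
2. **Section 3.1.10.** It points to 3.1.9 for DLTs and to 8.3 and 8.4 for other withdrawals, without ranking them.
3. **Section 8.4 itself.** The second-list item on events not recovering within 4 weeks has its own route for Sponsor approval. The pneumonitis and anaphylaxis items have none, so 8.4 does not supply the exception that 3.1.9 would need.

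The drafters did link the sections elsewhere. In 8.3.1, for Grade 2 pneumonitis, "the decision to reinitiate M and T upon resolution shall be based upon treating physician's clinical judgment", on condition that the event is not a DLT. The vaccine text has no such link.

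The secondary point concerns the scope of 8.4.

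- The first list gives no pneumonitis grade; the second starts at Grade 3. The text does not say whether the first covers the vaccine only and the second all study treatment.
- The first list is headed as withholding or postponing, yet its pneumonitis item discontinues.
- Neither pneumonitis item mentions attribution. Under 3.1.8, an event clearly caused by durvalumab or tremelimumab is managed under 8.3, whose pneumonitis rules concern those two drugs only. Whether the 8.4 vaccine rule then applies is not stated.

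**The case against.** The strongest reply is that a general, discretionary sentence in 3.1.9 should be read as subject to the specific rules in 8.4, to which 3.1.8 and 3.1.10 refer. That is a reasonable reading, but the text does not state it. The opposite is equally available: 3.1.9 deals specifically with what happens after a DLT and names the vaccine as the exception.

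A second reply is that the permission is narrow. This stands. Stopping is the default, and continuing requires the subject's best interest and agreement by the Investigator, the subject and the Sponsor. A reader might infer that a site could continue the vaccine on its own, or that risk would differ by site. The documents do not support that, because the Sponsor is a party to every such decision. The conditions limit how often the conflict arises but do not remove it.

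A third reply is that the two 8.4 lists are compatible: the first ends the vaccine and the second ends everything. Much of this stands. A reader might infer that 8.4 gives opposite answers for Grades 1 and 2. It does not, because absence from a list of prohibitions is not permission, and stopping the vaccine satisfies both lists. What remains is an unstated scope. Other second-list items are specific to the vaccine, such as re-exposure to BI 1361849, so the division into vaccine and all treatment is not clean.

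A reader might also see a clash with the 8.3.1 rule on Grade 2 pneumonitis. There is none; that rule governs durvalumab and tremelimumab, not the vaccine.

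**Conclusion.** The point holds for a defined set of events: related Grade 3 or higher pneumonitis, related Grade 2 pneumonitis not down to Grade 1 or lower within 3 days, and Grade 3 or higher related anaphylactic reactions that count as DLTs. The clearest case is Grade 3 or higher, where 8.4 prohibits continuation and 3.1.9 allows the vaccine by agreement. For the Grade 2 DLT, the opposing text is the first list's instruction to discontinue. Here the conflict rests on reading the absence of a grade as covering all grades.

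Two larger claims are not supported.

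- **That every confirmed pneumonitis is affected.** Grade 1 and quickly resolving Grade 2 events are not DLTs by the listed criteria. Events attributed to durvalumab or tremelimumab may fall outside 8.4 altogether. The documents give no expected pneumonitis rate for this trial, so a number of affected subjects would be guesswork, and the point does not need one.
- **That the primary tolerability result is weakened.** A DLT is counted when its criteria are met, before anyone decides about further vaccine. Subjects with a DLT in the evaluation period stay in the DLT population (Protocol 4.1.2, SAP 4.3). The SAP also tabulates adverse events leading to vaccine discontinuation separately (9.1.1) and summarises vaccine exposure (8.0).

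This should be corrected because a stated permission contradicts a stated prohibition on a matter of subject safety. It is not a flaw in the analysis.

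**What to change.** Reconcile the post-DLT sentence in Section 3.1.9, the DLT item in Section 3.1.10 and both lists in Section 8.4.

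- State which section takes precedence for BI 1361849 when an event is both a DLT and named in 8.4.
- State for each 8.4 list which drugs it covers.
- State whether the 8.4 pneumonitis rule applies when the event is attributed to durvalumab or tremelimumab.

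The choice of rule belongs to the sponsor and the drug providers; this review takes no position on it.

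The cost is a short protocol clarification and a letter to sites, with no new data or procedures. The documents do not say whether dosing has finished. If it has, the study report should record which rule was applied to any subject with one of these events.

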## 8.5 RECIST 1.1 and irRECIST Guidelines

The Response Evaluation Criteria in Solid Tumors (RECIST) guidelines were revised in 2009 as RECIST 1.1.(31) These guidelines have been the widely accepted criteria to assess response and progression in solid tumors; however, limitations have been noted in the use of RECIST 1.1 for immunotherapy trials. With immunotherapeutic agents, clinical trials have shown that complete response, partial response, or stable disease status can still be achieved after an initial increase in overall tumor burden, and regression of initial lesions may occur despite development of new lesions. The Immune-related Response Criteria (irRC) were developed to address the need for response criteria in an immunotherapy setting.(32) The main difference with irRC was that it considered the subject's total tumor burden at each subsequent assessment and required confirmation of suspected disease progression with subsequent imaging, approximately four weeks later. In addition, a greater number of lesions (10 vs. 5) were measured in a bidimensional manner instead of unidimensionally as in RECIST 1.1. In 2013, Nishino et al. demonstrated that immune-related response criteria using unidimensional measurements were highly concordant with the bidimensional results of irRC, but with less measurement variability.(33) Based on these findings and in order to utilize both the established criteria of irRC and RECIST 1.1, the two systems have been adapted, modified, and combined into the Immune-related Response Evaluation Criteria in Solid Tumors (irRECIST).(34) The adapted irRECIST criteria are modifications to the irRC, incorporating the findings of Nishino et al. and the advantages of RECIST 1.1 while overcoming the shortcomings of each of the other guidelines.

The guidelines for RECIST 1.1 are summarized below, followed by a summary for irRECIST.

